7.3 Enrollment Controls

Enrollment will be monitored to ensure that no more than the specified number of subjects is enrolled. An electronic data capture (EDC) system will be used and the system will be monitored to ensure maximum enrollment is contained. All sites will be notified when enrollment is near the target (within 15 subjects to maximum enrollment). The electronic database will display a message announcing that target enrollment is reached.

8 Study Procedures

8.1 Written Informed Consent

A sample ICF is provided in **Appendix C** for the Investigator to prepare for use at the site. The written Informed Consent documents must be prepared in the language(s) of the potential subject population. The ICF must be approved by the study Institutional Review Board (IRB)/Ethics Committee (EC) and a copy provided to Stryker Neurovascular. Modifications to the form must be approved by Stryker Neurovascular prior to implementation. The document version must be identified on the ICF to maintain version control.

Written Informed Consent must be obtained for all subjects prior to data entry into the Trevo Retriever Registry electronic database. The subject or the subject's legally authorized representative (LAR) will be asked to sign the ICF. Consent should be obtained pre-procedure but depending on subject's acuity the consent may be obtained up to seven days post-procedure. No data may be entered into the database until written consent has been obtained. In the absence of informed consent, an IRB/EC approved waiver of consent and executed data use agreement must be in place.

Study personnel should document the consent process in the subject's medical record per Good Clinical Practice (GCP). The subject or LAR is to be provided a copy of the signed ICF.

8.2 Pre-procedure Assessment

The following pre-procedure data will be collected:

- Confirmation that the subject meets the Inclusion/Exclusion criteria

Trevo[®] Retriever Registry

- Demographics and medical history, including blood pressure and pre-stroke mRS
- Baseline Labs (PT, PTT, platelets, INR, glucose, pregnancy test if applicable)
- Baseline Medications
- Neurological examination including mRS and NIHSS assessments
- Determination of intracranial lesion location and if clot location is amenable for treatment utilizing the Trevo Retriever

8.3 Trevo Thrombectomy Procedure

Physicians should follow the most current IFU at all times with regards to the device compatibility, preparation and the recommended retrieval procedure. The Trevo thrombectomy procedure should be performed per the following general steps:

- Gain arterial access with 6F (or larger) Guide Catheter or BGC
- Place the appropriate Trevo Microcatheter distal to the clot
- Use of intermediate DAC for added support is optional
- Load the Trevo Retriever into the compatible Trevo Microcatheter using the insertion tool and advance to site of occlusion
- Pull back on the Trevo Microcatheter to unsheath the Trevo Retriever within the clot
- After deploying the Retriever within the clot, visualize strut expansion and allow sufficient time for clot integration into the Retriever (approximately 5 minutes)
- If using a BGC, inflate the balloon to arrest flow
- Slowly pull the Trevo Retriever and Trevo Microcatheter back as a unit
- As the Trevo Retriever and microcatheter are being removed, begin vigorous aspiration through the guide catheter until the Trevo Retriever is removed from the subject

NOTE: Do not perform more than six (6) retrieval attempts in the same vessel. This total number applies for any combination of retrieval devices.

Immediately after each retrieval attempt with the Trevo Retriever, perform biplane angiography in order to assess the vessel patency in the neurovascular tree that is being treated. The same angiogram orientation should be used before and after the Trevo Thrombectomy procedure to assess the reperfusion status of the vessel(s).

- If reperfusion has been successful with the Trevo Retriever (recommended modified TIC1 score in the territory treated is $\geq 2b$) the Trevo thrombectomy procedure should be stopped and no further interventions performed.
- If reperfusion has not been successful (recommended modified TIC1 score in the territory treated is $\geq 2b$) with the Trevo Retriever continue with additional retrieval attempts (up to the maximum allowed per the IFU). At any time during the procedure, adjunctive treatment (rescue therapy) may be initiated if deemed appropriate by the treating physician.

Trevo[®] Retriever Registry

If adjunctive treatment (rescue therapy) is used AFTER the Trevo Retriever, biplane angiography should be performed immediately afterwards in order to reassess vessel patency and determine the effect of the adjunctive rescue treatment. The last angiogram prior to the use of rescue therapy will be considered when rating post-Trevo Retriever reperfusion.

NOTE: The Trevo thrombectomy procedure should be terminated if any of the following occur:

- Neurological deterioration or alteration in function is detected leading to the suspicion of an intracranial hemorrhage.
- Evidence of intracranial hemorrhage on imaging is noted.
- The occlusion is refractory to six retrieval attempts in a single vessel.

Neurological deterioration or alteration in function leading to the suspicion of an intracranial hemorrhage will necessitate an emergent head CT or MRI scan. At the discretion of the treating physician, this evaluation may also include angiography or other diagnostic tests to determine the etiology of the clinical alteration. Management of an intracranial hemorrhage will be performed according to each institution's usual practice.

8.4 24 hours (-6/+24) post procedure

The following data will be collected at 24 hours (-6/+24) post procedure:

- NIHSS (see **appendix G**)
- SAEs related to the device or procedure.
- For all subjects who expire prior to the 24 hours (-6/+24) assessment, available information regarding the primary cause of death and date/time of death will be recorded, as well as, whether the subject was made “do not resuscitate” (DNR) or “comfort care only” prior to expiration.

Any death or SAE must be reported to Stryker Neurovascular within 24 hours of becoming aware by eCRF completion.

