2.1 TREVO Study

The TREVO study was a post marketing prospective, multi-center, single arm study performed at seven sites in Europe designed to quantify the performance of the Trevo Retriever in providing revascularization and clinical benefit to subjects experiencing a large vessel occlusion within 8 hours of symptom onset. The devices used in the study were the Trevo 4 x 20 mm, Trevo Pro 4, and Trevo 3 x 10 mm.

Sixty (60) subjects were enrolled between February 2010 and August 2011. Revascularization and intracranial hemorrhage at 24 hours were independently assessed by a central core lab. A Clinical Events Committee (CEC) independently reviewed all protocol-defined safety endpoints to determine relationship to the device and the procedure, and the causes of all deaths.

The primary endpoint in TREVO was defined as angiographic revascularization as measured by the independent core lab using the TICI scale. Success was defined as a final TICI score of 2a or better. Post procedure, successful revascularization was achieved in 91.7% of subjects. In the TREVO study, operators were not restricted from using intra-arterial (IA) lytic, but it was only used in 10% of cases.

Trevo[®] Retriever Registry

The secondary endpoints in TREVO were 90-day good clinical outcomes (defined as mRS of 0-2), 90 day mortality, device-related serious adverse events (DRSAEs) and symptomatic intracranial hemorrhage (SICH) at 24 hours (see **Table 1**).

Coincidentally, the rate of DRSAEs and SICH endpoints were both 5% (3/60), however the rates are not cumulative. One of the three SICHs was a DRSAE, while the other two were procedure-related. As mentioned above, one of the DRSAEs resulted in SICH while the other two DRSAEs were associated with subarachnoid hemorrhage (SAH).

Table 1. TREVO Study Primary and Secondary Endpoints ^[10]

Primary Effectiveness Endpoint	TREVO (N=60 subjects)
Revascularization	91.7% (55/60)
Secondary Endpoints	
90-Day Good Outcome (mRS = 0-2)	55.0% (33/60)
90-Day Mortality	20.0% (12/60)
Device-Related SAEs (DRSAEs)	5.0% (3/60)
SICH at 24 Hours (SITS-MOST)	5.0% (3/60)
SICH (ECASS III definition)	8.3% (5/60)

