2.2 TREVO 2 Study

The TREVO 2 study was an IDE trial designed to support a 510k application for FDA clearance in the U.S. The trial^[8] enrolled 178 subjects between February 3, 2011 and December 1, 2011 at 26 sites in the United States and one site in Spain. The subjects were randomized 1:1 to Trevo (N=88) or Merci (N=90) and were stratified by age and baseline NIHSS to ensure balance in the two arms. The devices used in the study were the Trevo 4 x 20 mm in 10 subjects, and the Trevo Pro 4 in 78 subjects. The subjects treated with Merci[®] Retrievers were treated with commercially available product, at the discretion of the treating physician.

Trevo[®] Retriever Registry

The results for the primary effectiveness and safety endpoints are shown in the **Table 3**, and the results of the secondary endpoints are shown in **Table 4**.

Table 3. Primary Endpoint Results per the TREVO 2 (ITT population) ^[11]

Endpoint	Trevo (N=88)	Merci (N=90)	Difference [95% CI] ^a	p-value
Primary Effectiveness Endpoint:				
Post-Device Revascularization Success (TICI 2a+)*	86.4% (76/88)	60.0% (54/90)	26.4% [13.2%, 39.0%]	< 0.0001 ^b < 0.0001 ^c
Primary Safety Endpoint:				
Composite Events ***	14.8% (13/88)	23.3% (21/90)	-8.6% [-20.7%, 3.2%]	0.1826 ^d
Vessel Perforation	1.1% (1/88)	10.0% (9/90)	-8.9% [-17.0%, -2.2%]	
Intramural Arterial Dissection	0.0% (0/88)	1.1% (1/90)	-1.1% [-6.1%, 3.1%]	
Symptomatic ICH	6.8% (6/88)	8.9% (8/90)	-2.1% [-10.7%, 6.4%]	
Embolization to Previously Uninvolved Territory	6.8% (6/88)	4.4% (4/90)	2.4% [-5.0%, 10.3%]	
Access Site Complication Requiring Surgical Repair or Blood Transfusion	2.3% (2/88)	1.1% (1/90)	1.2% [-4.0%, 6.9%]	
Mortality within 24 hours	2.3% (2/88)**	0.0% (0/90)	2.3% [-1.9%, 7.9%]	
In vivo Device Failure	0.0% (0/88)	0.0% (0/90)	0.0% [-4.1%, 4.2%]	
Other PR-SAE	0.0% (0/88)	0.0% (0/90)	0.0% [-4.1%, 4.2%]	

* Administration of IA t-PA was counted as a failure for post-device revascularization.

** One death that occurred within 24 hours was related to the device, the other was attributed to the index stroke.

***Patients who experienced more than one safety event are counted only once in the composite safety endpoint.

a: By normal approximation; b: non-inferiority hypothesis using Blackwelder's method with non-inferiority margin of 10%; c: One-sided Wald test of superiority; d: Fisher's exact test.

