5.1 Primary Data point

Revascularization status at the end of the procedure using the modified TIC1 score.

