Procedure-Related Serious Adverse Event (PRSAE):	Procedure-related events that include, but are not limited to vascular perforation or intramural arterial dissection, symptomatic ICH, embolization to a new territory, or access site complication requiring surgical repair or blood transfusion, intra-procedural death, or device failure (e.g. in vivo breakage).

STRYKER CONFIDENTIAL - THIS DOCUMENT CONTAINS CONFIDENTIAL AND PROPRIETARY INFORMATION THAT IS THE PROPERTY OF STRYKER CORPORATION. NEITHER THIS DOCUMENT NOR THE INFORMATION HEREIN MAY BE REPRODUCED, USED, OR DISCLOSED TO ANY THIRD PARTY WITHOUT THE PRIOR WRITTEN CONSENT OF STRYKER CORPORATION.
CDM 1000023 Rev. AC

Trevo[®] Retriever Registry

Protocol Deviation:	This protocol does not require specific interventions, therefore the term deviation will only be used to describe the following situation: Failure to obtain informed consent per Good Clinical Practices (GCP).
Serious Adverse Device Effect (SADE):	An adverse device effect that has resulted in any of the consequences characteristic of a serious adverse event or that might have led to any of these consequences if suitable action had not been taken or if circumstances had been less fortunate.
Serious Adverse Event (SAE):	An adverse event in a research subject that led to a death, or led to a serious deterioration in the health of the subject that resulted in a life-threatening illness or injury, or resulted in a permanent impairment of a body structure or a body function, or required in-subject hospitalization or prolongation of existing hospitalization, or resulted in medical or surgical intervention to prevent permanent impairment to body structure or a body function. SAEs are a subset of AEs.
Subarachnoid Hemorrhage (SAH):	Bleeding into the subarachnoid space - the area between the arachnoid membrane and the pia mater surrounding the brain.
Symptomatic ICH (SICH):	The primary protocol definition is adapted from ECASS III as any apparently extravascular blood in the brain or within the cranium that is associated with clinical deterioration as defined by an increase of four points or more in the NIHSS or that led to death and was judged to be the predominant cause of a neurologic deterioration. SITS-MOST definition is any PH-2, defined as dense hematoma > 30% total of the infarcted area with substantial space-occupying effect or any hemorrhage area outside the infarcted area.

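### Does the repeated ≥ 2b parenthesis in Protocol section 8.3 leave the stop-or-continue instruction contradictory?

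*Protocol*

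**What the plan says.** Section 8.3 of the Protocol lists general steps for the thrombectomy procedure, opening with the statement "Physicians should follow the most current IFU at all times". After each retrieval attempt, angiography is done and one of two bullets applies.

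- The first bullet covers the case where restoring flow "has been successful with the Trevo Retriever (recommended modified TIC1 score in the territory treated is $\geq 2b$) the Trevo thrombectomy procedure should be stopped".
- The second bullet says "If reperfusion has not been successful (recommended modified TIC1 score in the territory treated is $\geq 2b$) with the Trevo Retriever continue", followed by further attempts up to the maximum in the instructions for use. It also lets the treating physician start rescue therapy at any time.

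The parenthesis is the same in both bullets. Elsewhere, section 5.1 gives the primary data point as "Revascularization status at the end of the procedure using the modified TIC1 score", without a success cut-off. Appendix E defines grades 0, 1, 2a, 2b and 3 but does not label any of them a success. Section 8.3 also says which image counts if rescue therapy is used: "The last angiogram prior to the use of rescue therapy will be considered when rating post-Trevo Retriever reperfusion".

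**The concern.** The two bullets have opposite premises and opposite actions, yet the same score is printed in each. A reader who looks only at the score would find that a grade of 2b or 3 points both to stopping and to continuing, and that a grade of 0, 1 or 2a points to neither. These instructions are consulted during an intracranial procedure, and the primary data point is the score when that procedure ends. If operators really were sent in different directions by the text, the number of passes and the final score could differ between sites for reasons unrelated to the device.

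The rest of the protocol offers no direct cross-check. Section 8.3 is the only place that attaches a success score to this registry, since section 5.1 and Appendix E give none.

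**Working it through.** The protocol states no figure to reproduce here, so the check sets the two bullets side by side on the Appendix E scale.

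**Inputs**
- Grades (Appendix E): {0, 1, 2a, 2b, 3}, 5 in all.
- Score printed in both bullets (section 8.3): ≥ 2b, that is {2b, 3}.
- Main clause of the first bullet: reperfusion successful, so stop.
- Main clause of the second bullet: reperfusion not successful, so continue. As the negation of the first bullet this is {0, 1, 2a}.

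**Three readings of the second parenthesis**

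| Reading | Stop | Continue | Overlap | Gap |
|---|---|---|---|---|
| A. It repeats the recommended benchmark for success | {2b, 3} | {0, 1, 2a} | 0 | 0 |
| B. The symbol is a slip for its complement (< 2b) | {2b, 3} | {0, 1, 2a} | 0 | 0 |
| C. It states the score observed in the failed case | {2b, 3} | {0, 1, 2a} ∩ {2b, 3} = empty | 0 | 3 |

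Readings A and B give the same instruction: 2 grades stop, 3 grades continue, and 2 + 3 = 5. Not knowing which of the two was meant changes nothing.

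Reading C is the only one that creates a problem, and it defeats itself. It makes the continue bullet apply to 0 of 5 grades, so the protocol would describe further attempts that could never be triggered. It also sits badly with the word recommended, which describes a target and not an observation. The conflict in which 2b and 3 lead to both actions requires a further step: ignoring the main clauses altogether, although they are what tell the two bullets apart.

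**Does anything downstream depend on it?**
- Primary data point: the modified TICI score itself at the end of the procedure, with no cut-off in section 5.1. Its definition does not use the section 8.3 threshold.
- Rating of the device alone when rescue is used: fixed by the angiogram rule quoted above, independently of the two bullets.
- Analysis population: section 9.2 depends on consent and on deployment of the retriever, not on the score reached.
- Sample size: section 9.1 makes no power estimate, so no error rate is affected.

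**The case for a change.** The strongest contrary case is that a stop-or-continue instruction should not have to be interpreted. The parenthesis follows directly on the words saying reperfusion was not successful and, grammatically, seems to describe that case. Section 17.3 tells investigators not to depart from the protocol except in an emergency, so the wording of section 8.3 carries some weight. A correction would take one line.

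Part of this stands: the sentence is awkward, and the sponsor could reconcile the two bullets when the protocol is next revised. It does not amount to a contradiction in the plan. The bullet immediately above supplies the benchmark, and the opposite main clauses assign every grade to one action. Section 8.3 presents its list as general steps, calls the score recommended and defers to the instructions for use. Appendix B adds "This protocol does not require specific interventions" and confines the term deviation to consent failures, which weakens the argument from section 17.3.

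A misread symbol also cannot be excluded, because the text was extracted by machine and the same parenthesis shows TICI as TIC1. The identical symbol in both bullets makes this less likely, but only the source PDF could settle it.

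**Conclusion.** The concern does not hold as a fault in the plan. The repeated parenthesis is a clerical blemish whose intent can be recovered from the text. Under both workable readings the grades split 2 to stop and 3 to continue, with 0 overlapping and 0 unassigned. The reading that produces a conflict leaves the continue bullet with 0 of 5 grades and is not a plausible way to use the section.

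No effect on conduct, number of passes, primary data point, analysis population or conclusions can be derived from the protocol, so changing the wording would bring no statistical gain.

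This rests on two assumptions: that the second bullet is meant as the negation of the first, and that any slip lies in the symbol and not in the grade printed beside it. The conclusion concerns only how the two bullets fit together. It is not an opinion on which threshold should govern the procedure.

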8.5 Discharge/Day 5-7 (whichever comes first)

A subject may be discharged from the hospital when clinically stable, at the Investigator's discretion. The following data will be collected at between Day 5-7 (if patient remains in the hospital) or at Discharge, whichever occurs first:

- NIHSS (see **appendix G**)
- mRS (see **appendix F**)
- SAEs related to the device or procedure
- Subject disposition at time of discharge
- For all subjects who expire prior to the Day 5-7/Discharge assessment, available information regarding the primary cause of death and date/time of death will be recorded, as well as, whether the subject was made DNR or “comfort care only” prior to expiration.

Trevo[®] Retriever Registry

Any death or SAE must be reported to Stryker Neurovascular within 24 hours of becoming aware by eCRF completion

8.6 Post Discharge Follow-up

The designated staff at the clinical site will review the study requirements with the subject to maximize compliance with the follow-up schedule. The staff will instruct subjects to return for follow-up assessments according to the study Time and Events Schedule in **Appendix D**. Study staff should establish a date for the follow-up visits with the subject and if possible, schedule the visits at the time of hospital discharge.

The study will be considered complete after all subjects have completed the Day 90 \pm 14 follow-up assessments. Requirements of each follow-up evaluation are detailed below.

8.6.1 Day 30 (+ 14)

At Day 30 (+14 days) the following study assessments should be performed:

- mRS (see **Appendix F**) - A telephone assessment is conducted
- SAEs related to the device or procedure
- For all subjects who expire prior to the Day 30 assessment, available information regarding the primary cause of death and date/time of death will be recorded, as well as whether the subject was made DNR or “comfort care only” prior to expiration.

Any deaths or SAE must be reported to Stryker Neurovascular within 24 hours of becoming aware by eCRF completion.

8.6.2 Day 90 (\pm 14)

At Day 90 (\pm 14 days) the following study assessments should be performed:

- mRS score (see **Appendix F**) - If subject is unable to return to the clinic for the Day 90 visit, a telephone mRS assessment is preferable to no assessment
- SAEs related to the device or procedure
- De-identify copies of health economic forms such as completed UB-04 Claims Forms, or equivalent claims forms per Country will be provided to Stryker with the registry subject number of the forms
- For all subjects who expire prior to the Day 90 assessment, available information regarding the primary cause of death and date/time of death will be recorded, as well as whether the subject was made DNR or “comfort care only” prior to expiration.

Any death or SAE must be reported to Stryker Neurovascular within 24 hours of becoming aware by eCRF completion.

9 Statistical Methods

9.1 Sample Size Estimate and Justification

There will be no sample size/or power estimation for this single-arm registry.

In order to conduct sub-group analyses and detect rare complications, of real world data a sample size of 2000 will provide more data for the further subgroup analysis. With total 2000 subjects, additional analysis of comparing TICI scores or 90 days mRS among the different locations could be carried out. Since recent positive data released from MR CLEAN and three other stent retriever randomized trials, there are more research questions to be answered such as how the time to treat will affect the patient outcome and how image screening may contribute to patient selection. Data analysis will be performed under guidance from the Study PIs, Steering Committee, and Sponsor.

9.2 Analysis Populations

The Intent-to-treat principle will be followed to define the analysis population. All of the subjects who signed the informed consent and in whom Trevo Retriever was deployed through the microcatheter are considered enrolled and will be included in the analyses.

Sub-group analyses for the Registry will be performed under guidance from the Study PIs, Steering Committee, and Sponsor.

Day 90 outcomes will be compared to pre-stroke mRS status, baseline imaging and time of symptom onset to treatment. The first interim analysis will be performed after 300 subjects are enrolled and the results will be reported. Additional interim analyses and data reporting will occur throughout the study enrollment period.

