STRYKER CONFIDENTIAL - THIS DOCUMENT CONTAINS CONFIDENTIAL AND PROPRIETARY INFORMATION THAT IS THE PROPERTY OF STRYKER CORPORATION. NEITHER THIS DOCUMENT NOR THE INFORMATION HEREIN MAY BE REPRODUCED, USED, OR DISCLOSED TO ANY THIRD PARTY WITHOUT THE PRIOR WRITTEN CONSENT OF STRYKER CORPORATION.

CDM 1000023 Rev. AC

Trevo[®] Retriever Registry

Table 4. Secondary Endpoints in TREVO 2 (ITT population) ^[11]

Endpoint	Trevo (N=88)	Merci (N=90)	Difference [95% CI] ^a	p-value
Time to Revascularization (mins) ^b Mean ± SD (N) Median (min, max)	47.8±44.2 (79) 34.0 (6.0, 209.0)	47.3±38.8 (81)40.0 (4.0, 207.0)	0.5 [11.4%] ^c	< 0.0001 ^d 0.5326 ^e
90-Day Good Outcome (Modified Rankin Score 0-2)	40.0% (34/85)	21.8% (19/87)	18.2% [4.2%, 31.7%]	0.0130 ^f
90-Day Mortality	33.0% (29/88)	23.6% (21/89)	9.4% [-4.2%, 22.7%]	0.1845 ^f
Asymptomatic ICH at 24 hours	40.9% (36/88)	53.3% (48/90)	-12.4% [-27.1%, 2.5%]	0.1017 ^f
Neurological Deterioration at 24 hours ^g	15.9% (14/88)	22.2% (20/90)	-6.3% [-18.4%, 5.5%]	0.3418 ^f

a: By normal approximation; b: Time to Revascularization was defined as the time from the start of the embolectomy procedure to achieving durable TIC1 2a or better or to the end of the procedure if TIC1 2a was not achieved. Subjects who had a baseline TIC1 score of 2a or did not have a study device used are excluded from this analysis (7 cases in Trevo arm, 8 cases in Merci arm); c: Per hypothesis testing setup, one-sided 95% upper confidence interval is used; d: One-sided Student's t-test of non-inferiority test with non-inferiority margin of 0.5 hours; e: One-sided Student's t-test of superiority test; f: Fisher's exact test; g: Defined as a four or more point increase in the NIHSS at 24 hours as compared to the baseline.

[figure not shown]
Overall the results of the TREVO and TREVO 2 trials demonstrate revascularization efficacy and safety of the Trevo Retriever.

3 Study Device Description

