6.1 Method of Enrollment

Clinical data points will be evaluated in all subjects who meet the inclusion/exclusion criteria and where Trevo Retriever is used as the initial mechanical thrombectomy device to remove thrombus from the neurovasculature in the setting of acute ischemic stroke. For purposes of this registry, enrollment occurs when the Trevo Retriever is deployed through the compatible Microcatheter into the neurovasculature as the first mechanical neuro-thrombectomy device used to remove the thrombus.

A Screening and Enrollment Log will be maintained by each site to document basic information such as date screened and reason for screen failures for subjects who fail to meet the study eligibility criteria. In order to avoid bias, if a center chooses to participate in the Trevo Registry, every effort should be made to include all Trevo cases performed over a given duration of time in the registry. No site will be allowed to enroll more than 15% (300 subjects) of the entire maximum study population unless first approved by Stryker.

7 Study Population

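### The analysis set is labelled intent-to-treat but is a consented, Trevo-deployed set, so the revascularization rate is conditional on deployment and no count of undeployed attempts is assured

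*Protocol*

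**What the plan says.** Section 9.2 of the protocol opens its definition with: "The Intent-to-treat principle will be followed to define the analysis population". The operational rule follows at once: "All of the subjects who signed the informed consent and in whom Trevo Retriever was deployed through the microcatheter are considered enrolled". Those subjects form the analysis set.

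Section 6.1 fixes the moment of entry in the same terms: "enrollment occurs when the Trevo Retriever is deployed through the compatible Microcatheter into the neurovasculature as the first mechanical neuro-thrombectomy device". As a safeguard against bias, the section adds that "every effort should be made to include all Trevo cases performed over a given duration of time in the registry". Each site keeps a Screening and Enrollment Log of basic information, for example the screening date and the "reason for screen failures for subjects who fail to meet the study eligibility criteria".

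Three other provisions bear on the point:

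- The objective (Section 4.1) is real-world performance of the device.
- The primary data point (Section 5.1) is modified TICI at the end of the procedure.
- Section 8.3 lets rescue therapy start at any time. It rates post-Trevo reperfusion separately, on the last angiogram before rescue.

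**The concern.** Intent-to-treat means that membership is settled by the intention to treat and not by what happens afterwards. Deployment happens afterwards, and it is partly a result of how the device performs: Section 8.3 lists advancing the retriever to the occlusion and unsheathing it in the clot as steps of the Trevo procedure itself. An attempt that fails at either step does not lead to enrollment.

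The label therefore claims a property that the design does not have. A reader of the registry report would take an intent-to-treat rate to cover all cases in which a Trevo was the first choice, whereas it would cover only those in which the device reached the clot and was opened. For a registry meant to show real-world performance, failed delivery is part of the answer. If such cases are neither in the denominator nor tallied beside it, the reader cannot judge how far the two rates differ.

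**Working it through.** **Step 1: who is in the set.** The rule in Sections 6.1 and 9.2, applied to a consenting patient for whom a Trevo is the first device introduced:

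| What happens | Enrolled (6.1) | Analysed (9.2) |
|---|---|---|
| Trevo advanced, deployed, clot retrieved | yes | yes |
| Trevo advanced, deployed, clot not retrieved | yes | yes |
| Trevo introduced, cannot be advanced to the occlusion | no | no |
| Trevo advanced, cannot be deployed | no | no |

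Retrieval failures stay in the denominator. Delivery and deployment failures do not.

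**Step 2: what this can do to the rate.** The protocol states no expected rate, no delivery-failure rate and no sample-size derivation (Section 9.1), so there is no figure of the plan to reproduce. The inputs are:

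- p, success rate among deployed cases: 76/88 = 86.4%, the Trevo arm in Table 3. It serves only as a plausible value. The registry states none.
- f, share of first-device attempts never deployed: not in the protocol; assumed 1% to 5%.
- s, end-of-procedure success among undeployed cases: not in the protocol; varied from 0 to 100%.
- n = 2000, the maximum enrollment.

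All-attempts rate = (1 − f) × p + f × s. The reported rate is p, so the difference is p − [(1 − f) × p + f × s] = f × (p − s).

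| f (assumed) | s = 0 | s = 50% | s = p | s = 100% |
|---|---|---|---|---|
| 1% | +0.9 | +0.4 | 0 | −0.1 |
| 2% | +1.7 | +0.7 | 0 | −0.3 |
| 5% | +4.3 | +1.8 | 0 | −0.7 |

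Entries are percentage points; plus means that the reported rate is higher than the all-attempts rate. Example: 0.05 × (86.4 − 0) = 4.3, so 86.4% among deployed cases corresponds to about 82.0% among all attempts.

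With p = 55/60 = 91.7% (Table 1) and s = 0, the difference is 0.9 points at f = 1% and 4.6 at f = 5%. The choice of p matters little.

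**Step 3: scale.** The 95% half-width at n = 2000 is 1.96 × √(0.864 × 0.136 / 2000) = 0.015, or 1.5 points. With s = 0 the difference reaches 1.5 points at f = 1.5/86.4 = 1.7%. In the worst case, then, a failure share of about 2% exceeds the sampling error.

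**The case against.** *Everyone enrolled is analysed, so renaming the set changes no number.* This is correct as far as it goes: the explicit rule is consistent between Sections 6.1 and 9.2, and nobody is dropped after enrollment. But that is so because enrollment itself waits for deployment. The selection happens earlier and is still there. The rate for the deployed set stands; the description of it does not.

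*The log already reaches these cases.* Inclusion criterion 2 requires the Trevo to be the initial device used, so a failed delivery followed by another device could be logged as a screen failure with its reason. The log's contents are also given only as examples. Section 14.4 further requires Trevo failures and malfunctions to be documented and reported. This weakens any claim that the cases are invisible. Even so, no category is named, a device that anatomy would not let pass need not be a malfunction, and nothing brings a tally into the report.

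*A statistical analysis plan may deal with it.* It may add a sensitivity analysis, but it cannot recover a count that sites were never asked to keep.

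*A reader might infer that the primary rate is overstated.* The documents do not establish this. The endpoint is read at the end of the procedure and rescue is allowed, so an undelivered case opened by other means ends revascularized. The difference can be zero or slightly reversed. Counting every undeployed case as a failure fits the pre-rescue rating in Section 8.3, but for the primary endpoint it is only a worst-case bound.

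*A reader might also infer that the TREVO 2 intent-to-treat set included patients without a device, so that the same label covers two populations.* The Table 4 footnote, where subjects who "did not have a study device used are excluded from this analysis", invites this. But Section 2.2 gives the devices used as 10 + 78 = 88 subjects, the whole Trevo arm. The footnote also pools that reason with a baseline TICI of 2a and does not split its 7 Trevo cases. Moreover, the registry plans no comparison with TREVO 2, whose rate was rated post-device. That argument should not be made.

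**Conclusion.** The point holds as one of labelling and reporting. Section 9.2 claims intent-to-treat for a set that is defined by consent and by actual deployment, and the protocol assures no reported count of attempts that ended before deployment. This runs against its own aim of including all Trevo cases.

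The effect on the primary rate is f × (p − s), and its size is unknown because the protocol gives neither f nor s. With p = 86.4% (illustrative), f = 1% to 5% (assumed) and s = 0, it is about 0.9 to 4.3 points too high. With s = 50% it is about 0.4 to 1.8 points. With s = p it vanishes, and with s above p it changes sign. The supportable statement is that the rate is conditional on deployment and may differ from the all-attempts rate. The rate for deployed cases is a valid figure once it is named as such.

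**What to change.** 1. In Section 9.2, replace the intent-to-treat wording with 'consented, Trevo-deployed set'. The rule itself need not change.
2. Add a category to the existing Screening and Enrollment Log (Section 6.1) for cases in which a Trevo was introduced as the first device but not deployed. Aggregate counts suffice.
3. Report that count, k, beside the primary result. With x successes among n deployed subjects, give the all-attempts range from x/(n + k) to (x + k)/(n + k). Label the lower end as a worst-case bound, not as an estimate. State also that the range is approximate, because the tally is not limited to consenting patients while n is.

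The cost is a change of wording, one tally per site and a lower bound that reads slightly less favourably than the headline rate. Enrollment, follow-up and the primary analysis are unaffected.
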